2.2 Secondary Objective

Aim 2a. To assess whether IMT affects an individual's perception of exertional dyspnea and leg fatigue during constant load cycling and a 16-km cycling time-trial.

We hypothesize that individuals will have a reduced perception of exertional dyspnea after IMT, compared to pre-training.

Aim 2b. To examine the effects of IMT on the deoxygenation of the respiratory and limb locomotor muscles during constant load cycling and a 16-km cycling time-trial.

We hypothesize the deoxygenation of the respiratory and limb locomotor muscles will be reduced after IMT.

Aim 2c. To examine the effects of IMT on femoral blood flow (FBF) of the limb locomotor muscles during constant load cycling.

We hypothesize the decrease in demand for respiratory muscle blood flow after IMT would elicit vasodilation of limb locomotor muscles and optimize blood flow after IMT. IMT has the potential to attenuate the respiratory muscle metaboreflex. By measuring femoral blood flow, it will help inform us whether this is the case - such that more blood flow goes to limb locomotor muscles after IMT.

Aim 2d. To examine the effects of IMT on operating lung volumes during constant load cycling and a 16-km cycling time-trial.

We hypothesize the operating lung volumes during exercise will be improved after IMT.

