2.0 Objective(s)

2.1 Primary Objective

Aim 1a. To examine the effect of flow-resistive inspiratory muscle training on the severity of exercise-induced bronchoconstriction (EIB) after inspiratory muscle training (IMT). More specifically, the pre- and post-values of the percentage drop in forced expiratory volume in 1 second (FEV₁) from the eucapnic voluntary hyperpnea (EVH) test before and after IMT will be measured.

We hypothesize IMT will reduce the severity of EIB. We anticipate there will be differences in the percentage drop in FEV₁ after EVH testing, resulting in a lessening of EIB severity.

Aim 1b. To examine the effects of flow-resistive inspiratory muscle training on the strength and endurance of the inspiratory muscles. More specifically, the pre-

to post-values of maximum inspiratory pressure and sustained maximum inspiratory pressure before and after IMT will be measured.

We hypothesize IMT will increase the maximum inspiratory pressure and sustained maximum inspiratory pressure post-training. We anticipate there will be differences in the MIP and SMIP values, resulting in the improvement of inspiratory muscle strength and endurance.

Aim 1c. Evaluate differences in constant load parameters and 16-km cycling time-trial completion time and power output before and after IMT.

We hypothesize power output will increase during constant load cycling after training. In addition, subjects time-trial time performance will improve and power output will increase after IMT.

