Constant Load & Time-Trial Cycling Exercise: Before exercise, the participant adjusted the seat height on the cycle ergometer (Velotron, Velotron® Racermate, Seattle, WA), and then were fitted with a facemask (Hans-Rudolph, Shawnee, KS) and flow probe connected to a metabolic cart (Vmax® Encore, Vyair Medical, Mettawa, IL) and a Polar HR Monitor (Polar, Helsinki, Finland) underneath the sternum. Each participant completed two constant-load (CL) exercises with a 5-minute rest period in between, one at 15% below the gas exchange threshold (GET; CL1) and another at 15% above the gas exchange threshold (CL2), corresponding to 85% $\text{VO}_{2\text{peak}}$ (42). Males warmed up for 5 minutes at 60W, followed by a 5-minute rest (42, 66). After the 5-minute rest period, participants cycled at 5W for 2 minutes, immediately followed by a predetermined moderate workload. The moderate and submaximal workloads are determined from their GETs, estimated from changes in breath values using the modified V-slope method (42). Each participant completed a familiarization time-trial (TT) to learn the cycle gearing system and to reduce any further learning effects (61, 67). The cycle ergometer recorded each participant's power output (PO), speed, and time to complete the time-trial (33). The ergometer allows participants to vary their resistance and power output, with an electronic gearing system during the 16-km TTs, simulating an actual performance scenario.

Ratings of exertional dyspnea & leg fatigue: During constant-load cycling and the cycling time-trial, three modified Borg scales (0-10) were placed at arm's length, comfortably reachable by the participant on the cycle ergometer. Participants were asked to indicate their ratings of perceived breathing intensity, 0 indicating "not noticeable" and 10 indicating "maximal intensity imaginable". Secondly, participants were asked to rate perceived breathing unpleasantness, with 0 indicating "not unpleasant" and 10 indicating "maximal unpleasantness imaginable". Lastly, participants were asked to rate leg fatigue, with 0 indicating "not fatigued at all" and 10 indicating "total fatigue and exhaustion". Ratings were recorded every 2 minutes during each of the 8-minute constant loads and every 4 km during the 16-km time-trial.

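### Aims 2a, 2b and 2d are read partly from a self-paced time-trial in which Aim 1c predicts more power; confirmed fixed-watt constant-load readings should carry these aims

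*Combined protocol and SAP*

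**What the plan says.** Section 2.2 sets three secondary aims in two kinds of exercise. Aim 2a concerns "perception of exertional dyspnea and leg fatigue during constant load cycling and a 16-km cycling time-trial", and Aims 2b (muscle deoxygenation) and 2d (operating lung volumes) name the same pair of settings. The hypotheses are directional: "individuals will have a reduced perception of exertional dyspnea after IMT, compared to pre-training"; "We hypothesize the deoxygenation of the respiratory and limb locomotor muscles will be reduced after IMT"; "We hypothesize the operating lung volumes during exercise will be improved after IMT". None of them adds a condition of equal work. Aim 2a gives no direction for leg fatigue.

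Section 2.1, Aim 1c, predicts that "subjects time-trial time performance will improve and power output will increase after IMT". The sentence before it reads: "We hypothesize power output will increase during constant load cycling after training". Section 3.1 likewise counts power, time and speed among the performance outcomes for the constant loads as well as the time-trial.

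Section 6.0 describes the time-trial as self-paced: "The ergometer allows participants to vary their resistance and power output, with an electronic gearing system during the 16-km TTs". On sampling it says: "Ratings were recorded every 2 minutes during each of the 8-minute constant loads and every 4 km during the 16-km time-trial". NIRS runs in both constant loads and in the time-trial. Inspiratory capacity manoeuvres are made at points that are not listed.

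Section 8.0 specifies a two-way ANOVA for each outcome, with time (pre, post) and group (IMT, sham), and treats the interaction as the main test of efficacy. It has no term for power or ventilation and does not rank constant-load against time-trial readings.

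**The concern.** The plan expects IMT to do two things in the same ride: raise the power the rider chooses, and lower responses that would ordinarily be expected to rise with power. A pre-post comparison at a given kilometre then mixes the effect of IMT at equal work with the effect of riding harder. If Aim 1c is right, the second part works against Aims 2a (dyspnea), 2b and 2d. If riders happen to go slower, it works in their favour and could look like a benefit.

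At stake is what the time-trial estimates and intervals for these aims mean. A small or null difference could not separate no effect from an effect spent on more power.

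**Working it through.** **Inputs.** From the documents: the aims, pacing and model above; a 16% dyspnea reduction in the cited study of pressure-threshold IMT in asthma (Section 1.0, cycling at about 70% of VO2max); f = 0.25, alpha = 0.05, 20 planned and 11 completed (Section 8.0). Assumed, because the documents give no value: how steeply dyspnea rises with power, the power gain, and the pre-post correlation rho.

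**1. The plan's own figure.** There is none for this point. The nearest is N = 20 for 80% power. For the 2 x 2 interaction, lambda = f² x N x m / (1 - rho), with m = 2 and df 1 and N - 2. At rho = 0.72, lambda = 0.0625 x 20 x 2 / 0.28 = 8.93 and power is 0.807. The required N is 34 at rho 0.5, 22 at 0.70, 20 at 0.72 and 18 at 0.75. The figure is attainable but depends on an unstated correlation. Nothing below rests on it being right or wrong.

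**2. Does the sham arm remove the problem?** It removes what both arms share, such as learning or a season's training. The power gain in Aim 1c is attributed to IMT, so it differs between arms and enters the time x group interaction.

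**3. Possible size (illustration only).** Let the equal-work dyspnea ratio be 1 - 0.16 = 0.84, let dyspnea scale as power to the exponent e, and let sham be unchanged. Net time-trial change = 0.84 x (1 + gain)^e - 1.

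| e | gain 2% | gain 5% | gain 8% | gain that gives exactly zero |
|---|---|---|---|---|
| 1 | -14.3% | -11.8% | -9.3% | 19.0% |
| 2 | -12.6% | -7.4% | -2.0% | 9.1% |
| 3 | -10.9% | -2.8% | +5.8% | 6.0% |
| 4 | -9.1% | +2.1% | +14.3% | 4.5% |

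The last column is (1/0.84)^(1/e) - 1. Smaller gains attenuate the effect and larger ones reverse it. In the other direction, with no equal-work effect, 5% less power and e = 2, the change is 0.95² - 1 = -9.75%, an apparent benefit from pacing alone.

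**4. Cost to the interaction test.** Same formula, with f halved to 0.125 if half the effect remains:

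| | rho 0.7 | rho 0.5 |
|---|---|---|
| N = 20, full effect | 0.779 | 0.562 |
| N = 20, half | 0.277 | 0.185 |
| N = 11, full effect | 0.481 | 0.317 |
| N = 11, half | 0.160 | 0.115 |

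(The N = 11 rows use the same formula, which does not allow for unequal arms; the split is not given.)

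**5. Are the constant loads at equal work?** Two facts suggest so: Section 6.0 calls the moderate load predetermined and derives both loads from the gas exchange threshold, and Section 5.0 lists no repeat incremental test after training. Against this, Aim 1c predicts higher constant-load power and Section 3.1 treats it as an outcome. The two cannot both stand. If watts were fixed, constant-load power is set by the investigator and cannot respond to training. If it could rise, the constant loads share the time-trial's problem.

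**The case against.** The strongest reply has four parts.

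- **The constant-load readings are already planned.** Section 2.2 names them, Section 1.0 speaks of deoxygenation during constant-load exercise, and Aim 2c (blood flow) is confined to it. This stands, and it narrows the gap to the lack of any ranking between the two settings and of any statement about watts.
- **Section 8.0 is already cautious.** It treats non-significant results as inconclusive and stresses effect sizes and intervals. So it would be wrong to say that a null time-trial result will be reported as no benefit. The caution does not cure the problem, however, because the estimate and its interval are themselves shifted.
- **The randomised time-trial comparison is valid for its own question,** the total effect of IMT at a self-chosen pace. This stands. It is a different question from whether dyspnea or deoxygenation is lower for the same work.
- **Not every response need rise with power.** Section 6.0 notes that tidal volume levels off at roughly 70% of inspiratory capacity, so the opposing push on V_T/IC may be weak near maximal effort. For leg fatigue the plan predicts no direction, so the opposing-direction argument in Aim 2a covers dyspnea only.

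A reader might also infer that every Borg reading is a separate test: 3 scales x 4 readings x 2 bouts + 3 x 4 = 36, or 36 x 0.05 = 1.8 expected false positives if all nulls are true. The documents do not establish this. Section 8.0 speaks of outcome variables, Section 3.2 mentions cumulative as well as separate scores, and neither says how serial readings are handled.

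**Conclusion.** The point holds in a limited form. Time-trial effects on dyspnea, deoxygenation and lung volumes may be attenuated, masked or reversed by an unknown amount, or imitated by a slower ride, and neither the model nor the sham arm separates these cases. This follows from the plan's own predictions together with the usual assumption that these responses increase with work.

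A reader might conclude that the predicted effects cancel. The documents do not support that: they give no slope and no expected power gain, and under the assumptions above exact cancellation needs a gain of 4.5% to 19.0%, depending on the exponent. Nor can the constant loads simply be called matched work; that is an inference which Aim 1c contradicts.

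The matter concerns secondary aims and interpretation. It should be corrected, but it does not touch the EIB severity or muscle-strength outcomes.

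**What to change.** 1. State whether each participant's post-training constant-load watts equalled the pre-training watts. Reconcile the answer with Aim 1c's constant-load prediction and with the constant-load performance outcomes in Section 3.1.
2. If watts were fixed, make the constant-load readings the main test of Aims 2a, 2b and 2d, compared between arms with the pre value as covariate. Label the choice post hoc, since 11 participants have already completed. CL2 is a reasonable lead bout: Section 6.0 says that in asthma/EIB hyperinflation shows itself mainly with severe obstruction or ventilation close to maximal, and CL2 is the harder load. Choose the time point from when readings were actually taken. A minute-8 value cannot be presumed for inspiratory capacity, whose timing is not given.
3. Report time-trial dyspnea, deoxygenation and V_T/IC descriptively, beside power at the same kilometre, as the total effect at self-chosen pace and not as tests of the directional hypotheses. Adding time-trial power as a covariate is no substitute, because that power is itself a predicted result of IMT.

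If watts were not fixed, the constant-load readings have the same limitation and should also be shown beside power.

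Cost: wording and re-presentation, with no new data if watts were fixed. The time-trial readings become descriptive. The covariate uses one degree of freedom (11 - 3 = 8 residual instead of 11 - 2 = 9, if all 11 contribute).

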3.0 Outcome Measures

3.1 Primary Outcome Measures

Outcomes of interest is the severity of exercise-induced bronchoconstriction (EIB), inspiratory muscle strength and endurance, and cycling performance.

EIB severity will be measured using the pre- and post-values of the percentage drop in forced expiratory volume in 1 second (FEV₁) obtained from the eucapnic voluntary hyperpnea (EVH) test before and after IMT.

Inspiratory muscle strength and endurance will be measured using the flow-resistive trainer device that will record maximum inspiratory pressure and sustained maximum inspiratory pressure for 8 weeks.

Cycling performance will be summarized by pre- to post-values in power output, time, and speed time to complete the time-trial and constant loads before and after IMT.

3.2 Secondary Outcome Measures

The secondary outcomes of interest include exertional dyspnea and leg fatigue, deoxygenation of respiratory and limb locomotor muscles, and operational lung volumes.

Exertional dyspnea and leg fatigue will be summarized by the separate and cumulative pre- and post-values of perceived scores before and after IMT.

Deoxygenation of respiratory and limb locomotor muscles will be summarized by pre- and post-values of respiratory and limb deoxygenation values via NIRS protocol before and after IMT.

Femoral blood flow will be summarized by pre- and post-values of blood flow values via Doppler ultrasound protocol before and after IMT.

Operation lung volumes to assess the degree of dynamic hyperinflation will be measured using flow volume loops and inspiratory capacity (IC) maneuvers. Respiratory mechanical constraint will be calculated by the tidal volume (V_T)/IC ratio to indicate the degree of dynamic hyperinflation, further implicating the potential of EFL ([56-60](#)).

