EIB may result in decreased exercise tolerance and performance, dynamic hyperinflation (DH), and decreased inspiratory muscle strength, leading to the onset of exertional dyspnea (ED) (19). ED is defined as the perception of the intensity and difficulty of breathing (15, 18, 19, 47-50). Common mechanisms leading to ED are chest tightness and work or effort of breathing (47). Work or effort of breathing has been theorized to be related to the respiratory system's central and peripheral coupling of muscle tone regulation, while chest tightness represents the degree of bronchoconstriction (15, 19, 47). The underlying mechanism responsible for ED is thought to involve dynamic hyperinflation (DH) of the lungs. DH occurs when there is a progressive increase in end-expiratory lung volume (EELV) during exercise with bronchoconstriction due to air trapping. This increase in EELV constrains tidal volume (V_T) closer to total lung capacity and the steeper, non-compliant region of the pressure-volume relationship between the lung and chest wall where elastic loading is greater to overcome (19, 32, 36, 37, 50-52). When there is a decrease between the volume of air to exhale, complete exhalation time, and frequency of inspirations, EELV increases (19, 32, 36, 37, 51), resulting in the immoderate elastic stretch of the inspiratory muscles forcing the muscles to function outside their optimal scope (15, 19, 49). The muscles then become weak, which results in a greater perception of dyspnea with the additional respiratory muscle work needed to overcome elastic loading forces (15, 19).

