Flow Limitation: At specific points during the exercise bout, participants were instructed to perform an inspiratory capacity (IC) maneuver, inspire to total lung capacity (TLC), and then exhale back to breathing normally. Respiratory mechanical constraint was calculated by the tidal volume (V_T)/IC ratio to indicate the degree of dynamic hyperinflation, further implicating the potential of EFL ([56-60](#)). In conditions characterized by pronounced mechanical constraint (e.g., COPD), IMT can reduce diaphragm activation and dyspnea ([76-78](#)). In asthma/EIB, however, resting spirometry is typically preserved and dynamic hyperinflation becomes prominent only under severe obstruction or near-maximal ventilation ([44](#), [51](#), [79-81](#)). Given that V_T generally reaches a mechanical ceiling when ~70% of IC is used and inspiratory reserve volume (IRV) approaches ~0.5–1.0 L, dyspnea intensity closely tracks this V_T /IC ratio rather than inspiratory strength per se ([56-60](#)).

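### V_T/IC is the only index derived for dynamic hyperinflation, but it also moves with tidal volume and can disagree with the rise in end-expiratory lung volume by which the protocol defines hyperinflation

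*Combined protocol and SAP*

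**What the plan says.** Section 1.0 (Background & Rationale) gives the definition: "DH occurs when there is a progressive increase in end-expiratory lung volume (EELV) during exercise with bronchoconstriction due to air trapping". It then describes the consequence for breathing pattern: "This increase in EELV constrains tidal volume (V_T) closer to total lung capacity".

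Section 3.2 (Secondary Outcome Measures) first lists the measurements: "Operation lung volumes to assess the degree of dynamic hyperinflation will be measured using flow volume loops and inspiratory capacity (IC) maneuvers". The next sentence gives the derived quantity: "Respiratory mechanical constraint will be calculated by the tidal volume (V_T)/IC ratio to indicate the degree of dynamic hyperinflation". Section 6.0 (Flow Limitation) repeats it in the past tense: "Respiratory mechanical constraint was calculated by the tidal volume (V_T)/IC ratio to indicate the degree of dynamic hyperinflation". On timing, Section 6.0 says only: "At specific points during the exercise bout, participants were instructed to perform an inspiratory capacity (IC) maneuver".

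Aim 2d in Section 2.2 covers the constant-load bouts and the 16-km time-trial. Its hypothesis is general: "We hypothesize the operating lung volumes during exercise will be improved after IMT". It names no variable and does not say which direction counts as better. Section 8.0 applies one group-by-time model to every outcome and says nothing specific to lung volumes.

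**The concern.** The definition and the derived index are different quantities. The definition concerns where the breath ends on expiration. The index compares the size of the breath with the room available for it. No section names IC, its change during exercise, or EELV as a derived outcome, so an analyst following the text would read the degree of hyperinflation from V_T/IC.

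That matters because training may alter breathing pattern. A deeper breath at the same EELV would look like more hyperinflation, and a shallower breath could hide a real rise in EELV. Section 1.0 presents hyperinflation as the mechanism thought to underlie exertional dyspnoea, so a misread result here would affect how the dyspnoea findings are explained.

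**Working it through.** The documents report no V_T, IC or EELV values, so there is no figure of the plan's own to reproduce. The check is algebra plus worked cases.

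**Inputs.** From the documents: hyperinflation is a rise in EELV (Section 1.0); the index is V_T/IC (Sections 3.2 and 6.0); V_T generally meets a mechanical ceiling at about 70% of IC (Section 6.0). Assumed for illustration: TLC 6.0 L, and the V_T and IC values below.

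**Formulas.**
- EELV = TLC − IC. With TLC constant, change in EELV = −(change in IC). V_T does not enter.
- Change in ln(V_T/IC) = change in ln(V_T) − change in ln(IC). The ratio moves against EELV in the hyperinflation sense whenever V_T changes proportionally more than IC in the same direction.

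**Worked cases.**

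| Case | V_T (L) | IC (L) | Change in EELV (L) | V_T/IC | Reading of the ratio |
|---|---|---|---|---|---|
| 1 | 2.0 to 2.3 | 3.0 to 3.0 | 0 | 0.667 to 0.767 | apparent worsening |
| 2 | 2.10 to 1.89 | 3.0 to 2.7 | +0.3 | 0.700 to 0.700 | worsening missed |
| 3 | 2.0 to 2.3 | 3.0 to 3.2 | −0.2 | 0.667 to 0.719 | wrong sign |
| 4 | 2.0 to 1.8 | 3.0 to 2.8 | +0.2 | 0.667 to 0.643 | wrong sign |
| 5 | 2.0 to 2.0 | 3.0 to 3.2 | −0.2 | 0.667 to 0.625 | right sign |
| 6 | 2.0 to 2.1 | 3.0 to 3.2 | −0.2 | 0.667 to 0.656 | right sign |

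**Where the sign turns.** If IC rises from 3.0 to 3.2 L (0.2/3.0 = 6.7%), the ratio rises once V_T exceeds 2.0 × 3.2/3.0 = 2.13 L, which is also a 6.7% increase. Below that, ratio and EELV agree, as in cases 5 and 6.

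**Dependence on the 70% ceiling.** Cases 1 and 3 end above 0.70, but the effect does not need that. At IC 3.0 L, V_T going from 1.8 to 2.0 L moves the ratio from 1.8/3.0 = 0.600 to 2.0/3.0 = 0.667 with EELV unchanged. Case 4 also stays below 0.70 throughout.

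**Plausibility.** Section 1.0 says a higher EELV constrains V_T, so V_T and IC may fall together, as in cases 2 and 4. Aim 1c expects power output to rise after training in the constant-load bouts and the time-trial. If higher power brings larger breaths, V_T rises for reasons unrelated to EELV. That link is an assumption; the documents give no figure for it.

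**The case against.** The strongest reply is that the plan ties hyperinflation to IC in the sentence just before the ratio, and calls the ratio mechanical constraint. On that reading the hyperinflation variable is under-specified, but IC has not been replaced, and nothing says IC will go unreported. This stands in part: IC is listed as a measurement. But the ratio is the only quantity the text calculates, and two sections say it shows the degree of hyperinflation.

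Second, V_T/IC is a reasoned choice. Section 6.0 says dyspnoea intensity tracks it, and that hyperinflation in asthma becomes prominent only with severe obstruction or near-maximal ventilation. In case 1 the inspiratory reserve (IC − V_T) falls from 1.0 to 0.7 L, so the ratio correctly registers more constraint. This stands, and is a reason to keep the ratio. It does not make the ratio a measure of EELV.

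Third, the cases are constructed, and case 2 needs V_T and IC to fall by the same 10%. Also, if the same constant-load workloads were used before and after training, shifts in V_T there could be limited. Both points stand as limits on likelihood. The documents do not say whether the workloads were repeated unchanged.

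A reader might go further and infer that Aim 2d as a whole will come out with the wrong sign. The documents do not support that. The aim concerns operating lung volumes broadly, with no variable or direction named, and cases 5 and 6 show the ratio agreeing with EELV when V_T is stable or changes proportionally less than IC.

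**Conclusion.** The point holds as a mismatch between a definition and the index derived for it. V_T/IC can mislead about hyperinflation in three ways: movement with EELV fixed, no movement when EELV rises, and movement in the opposite direction. How often this would happen in the trial cannot be judged from the documents. The sizes shown rest on assumed volumes, and EELV follows from IC only if TLC is constant; no TLC measurement is described.

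The consequence is confined to the hyperinflation part of one secondary aim. Section 8.0 reports 11 completers, calls the findings preliminary and treats non-significant results as inconclusive, which limits the harm of a flat result. It does not protect against a result in the wrong direction.

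It would also go too far to infer that change in IC from rest to the end of the second constant-load bout can simply be computed. The text does not document a manoeuvre at rest or at that point.

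**What to change.** In Sections 3.2 and 6.0:

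- Name IC as the dynamic hyperinflation variable (equivalently EELV = TLC − IC), and state that TLC is assumed constant.
- Compare it pre to post between arms at matched IC-manoeuvre points in both the constant-load bouts and the time-trial, and list those points. Where a resting IC was recorded, also give the change from rest.
- State that a higher exercise IC means less hyperinflation.
- Analyse it with the group-by-time model already in Section 8.0. This defect gives no reason for a different model.
- Report V_T/IC separately as mechanical constraint, and remove the wording that presents it as the degree of hyperinflation.
- If the variable is named after data collection, say so.

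The cost is wording in two sections and one extra derived secondary variable from IC manoeuvres the protocol already includes. The result will rely on the constant-TLC assumption. Because the time-trial is self-paced, matching on a point in the ride does not guarantee the same ventilation, so IC differences there need a more cautious reading.
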